# 11 Trial Intervention

# 11.1 PACE-HD (for the nested RCT)

Participants randomized to the exercise intervention (n=30) will receive an exercise and physical activity coaching intervention (PACE-HD) over a 12-month period. The PACE-HD intervention is based on interventions developed in two previous studies: *Exert-HD*, which utilized a 3 times per week aerobic and strengthening exercise program, and *Engage-HD* intervention, which utilized a coaching program with a purpose-designed workbook to facilitate physical activity and exercise uptake. The PACE-HD intervention is a physical activity behavioural change intervention (based on Engage-HD) that will specifically incorporate promoting aerobic and strengthening exercises based on the Exert-HD intervention. We aim to facilitate exercise uptake over a 12-month period in individuals with HD with the goal to increase both overall physical activity as well as aerobic and strengthening exercise, which has been shown to improve fitness and motor function in people with HD. The intervention will be delivered by licensed physical therapists with experience in delivering exercise-related activities and who will receive specific 1:1 training and ongoing monitoring to deliver the intervention.

The program will consist of 18 face-to-face coaching session (approximately 1 hour) to be held over the course of 12 months. The timing of these sessions will be determined by the participant in consultation with their coach. A coaching manual will be utilized to provide a structured approach to coaching sessions, which will focus on physical activity engagement (specifically aerobic and strengthening exercise) and adherence to exercise. In partnership with the coach, participants will develop physical activity goals that will be monitored and adjusted throughout the program. Participants will be asked to keep monthly physical activity diaries (via paper recording) to record the amount and type of physical activity involvement. These will be returned to local coordinating sites in stamped addressed envelopes provided. Participants will be given wearable activity monitors (Fitbit Charge 2) to be used throughout the 12-month period as a means to facilitate/monitor physical activity and sedentary behaviours. The schedule for receiving messages and the use of the FitBit data will be discussed collaboratively with the patient by the physical activity coach.

The 1:1 coaching intervention will take place in the participant's home or in a rehabilitation facility at each of the sites. Based on our extensive consultations with patients with HD and our prior research in this area, we know that patients with HD need flexibility in terms of access to exercise facilities, and this is critical to successful adherence to an exercise intervention in this population. Therefore, each participant will be provided with a choice of exercise equipment options including a ProForm 440

ES Exercise bike and other exercise equipment (e.g. hand-held weights, medicine balls, therabands) to be utilized for independent sessions. The ProForm bike has been tested in our previous studies, and has been found to be sufficiently sturdy and comfortable for this patient group, who can have excessive abnormal movements (chorea) as well as impaired postural control. Alternatively, participants can choose to exercise in a gym setting of their choice, or to utilize online resources such as exercise videos instead of a stationary bike.

#### 11.2 Adherence

The intervention will be provided by licensed physical therapists. Therapists will provide physical activity coaching, which will be modelled from/on the recently completed Engage-HD trial, and focuses on promoting strategies to maintain exercise using a workbook and participant-coach interaction that emphasizes relatedness, autonomy and competence. Caregiver support will be encouraged but is not required. Strategies that support the collaborative regulation theoretical underpinnings of the intervention will be a further focus of the intervention. We will also provide each participant with FitBit physical activity monitors, which can be used to provide reminders for exercising and feedback on physical activity levels to participants, but can also can provide feedback to the physiotherapists regarding the frequency, intensity and duration of independent sessions. For those participants who do not utilize mobile phones or personal computers (which are required to upload FitBit data), or would prefer not to utilize, we will ask permission to utilize text messaging to a caregiver or family member, or to phone the participant. We will also use exercise diaries developed in our feasibility studies, with the option for them to be completed online or via pen and paper. In addition, therapists will have direct contact with participants as needed throughout the course of the trial and will assist participants in setting up schedules and reminders for independent sessions. Exercise diaries will be reviewed by the therapist during every supervised session to facilitate adherence to the program and to monitor progression. Fidelity of the physical activity intervention will be measured using a combination of therapist self-report checklists (indicating whether the content of each of the sessions was consistent with what was specified in the protocol and training manual) and a self-assessment completed by the therapists, at least three times during the course of delivering the intervention to each participant, using a purpose developed rating scale. Although the timescale for completion of the therapist self-assessment will be decided upon by the therapist, we suggest completion after sessions 2, 6 and 15 Participant adherence will be assessed as part of the fidelity assessment in the process evaluation.

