# 5.3 Primary outcomes measure(s)

The primary outcome measures for this trial are focused on feasibility of the 12-month physical activity intervention.

- Recruitment rate will be assessed using site recruitment logs.
- Retention rate will be measured as the percentage of individuals who completed the intervention.
- Adherence rates will be defined as percentage of intervention sessions completed,
- Safety will be assessed through monthly documentation completed by therapists administering the intervention, which captures information on falls history, medication

changes, healthcare service use and hospital admissions (classified as serious adverse events).

- Fidelity of the interventions will be assessed via review of coach documentation and activity monitor data.
- Data completeness will be assessed by the percentage of data entered into the database.

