# Process Evaluation:

The process evaluation will utilise qualitative data (semi-structured interviews with intervention staff) and quantitative data (structured reflections by members of the research team delivering the intervention and a purpose developed fidelity questionnaire as well as data on completed visits) to assess fidelity (whether the intervention has been delivered as intended and as a measure of quality assurance), and the key mechanisms of change. Participants and their care-givers will be asked to complete a structured questionnaire that focusses on their views of the trial and of the intervention.

We will also attempt to contact any participants who drop out of the intervention to ascertain reasons for discontinuing.

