Intervention fidelity (participant diaries) (RCT only)			х						Х			
Intervention Fidelity [coach] (RCT only)			Х	Х								
Health and Falls Record (RCT only)			Х									
Adverse events			X									Х
Process Evaluation										X	Х	
Participant withdrawal			X	X								

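### Fidelity, a primary feasibility outcome, is given conflicting sources that overlap with adherence, and its self-assessment component is timed by the therapist being rated

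*Protocol*

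**What the plan says.** Section 5.3 introduces its list with "The primary outcome measures for this trial are focused on feasibility of the 12-month physical activity intervention" and gives fidelity and adherence separate entries. For fidelity it says "Fidelity of the interventions will be assessed via review of coach documentation and activity monitor data". Adherence is the percentage of intervention sessions completed.

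Section 11.2 says "Fidelity of the physical activity intervention will be measured using a combination of therapist self-report checklists". The checklist is filled in session by session, "indicating whether the content of each of the sessions was consistent with what was specified in the protocol and training manual". To these it adds a self-assessment on a purpose-built rating scale, done by the therapist at least three times per participant. On timing, "the timescale for completion of the therapist self-assessment will be decided upon by the therapist", with sessions 2, 6 and 15 offered as a suggestion. The section ends by placing participant adherence within the fidelity assessment.

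The Process Evaluation part of section 12 lists staff interviews, structured reflections by those delivering the intervention, and "a purpose developed fidelity questionnaire as well as data on completed visits".

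Table 3 describes the FitBit data as a record of adherence. Table 6 has a row "Intervention fidelity (participant diaries) (RCT only") and a separate fidelity row for the coach. Section 16.1.1 lists a staff fidelity checklist form and a home visit record for up to 18 visits.

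Section 15.1 says adherence, safety and fidelity will be summarised for the RCT. Its progression criteria refer only to drop-out.

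**The concern.** There are two problems.

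The first is that fidelity of delivery and participant adherence are different quantities, and the protocol does not keep them apart. A coach can deliver every session to the manual for someone who does little exercise in between, or the reverse. If monitor data, diaries or session attendance enter the fidelity figure in one section and the adherence figure in another, the result depends on which section the analyst follows. A reader of the report cannot then tell whether a low figure reflects the coaching or its uptake.

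The second is that one of the two measures in section 11.2 is completed by the rated person at moments that person chooses. Ratings made when delivery is going well would raise the average. A rating after session 3 for one participant and after session 15 for another also describe different stages of the programme. No later analysis can undo this, because timing is fixed when the data are collected.

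**Working it through.** The protocol gives no target, threshold, score or standard deviation for fidelity, so there is no fidelity figure to reproduce. The only precision figure, in section 14.3, concerns cohort retention: 1.96 × √(0.7 × 0.3 / 120) = 0.082, which agrees with the stated 8.2%. It has no bearing on fidelity.

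**Sources side by side**

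| Source | 5.3 | 11.2 | 12, Process Evaluation | Table 3 | Table 6 |
|---|---|---|---|---|---|
| Coach checklist or documentation | fidelity | fidelity | not named | – | fidelity (coach row) |
| Therapist self-assessment | could fall under coach documentation | fidelity | may be the questionnaire or the reflections | – | could fall under coach row |
| Activity monitor data | fidelity | not in the measurement sentence | not named | adherence (FitBit) | listed separately, without a fidelity label |
| Participant diaries | not named | used to support adherence and follow progression | not named | – | fidelity |
| Sessions or visits completed | adherence, a separate outcome | adherence placed inside fidelity | fidelity | – | – |

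The coach rows can be read as consistent. The last three rows cannot: monitor data, diaries and attendance each change label between sections.

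Section 5.3 also does not say which monitor it means. If it means FitBit, section 11.2 itself identifies "participants who do not utilize mobile phones or personal computers (which are required to upload FitBit data"), so that part of the measure would have no data for such participants.

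**Why the label matters.** Let a participant attend k of the 18 planned sessions, with c of them meeting the manual.

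- Adherence under 5.3 = k/18.
- Checklist fidelity under 11.2 = c/k.

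Take a hypothetical participant who stops after session 6, with every session delivered to the manual. Adherence is 6/18 = 33%, while checklist fidelity is 6/6. Once attendance is counted inside fidelity, as the end of 11.2 and the completed visits in section 12 imply, the 6/6 no longer stands alone as the fidelity result.

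**What therapist-chosen timing affects**

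- Checklist: it covers each session, so up to 30 × 18 = 540 records if everyone completes. Timing cannot be selected.
- Self-assessment: at least three per participant, so at least 30 × 3 = 90 if everyone completes. Timing is the therapist's choice.

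Only the second is open to selection. Section 11.2 does not say whether a self-assessment scores one session or delivery to date; on either reading the therapist chooses the moment. The upward shift would depend on how ratings vary between occasions and how closely the chosen moment tracks good delivery. The documents give neither.

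**Early stoppers.** With free timing, three self-assessments are impossible only for participants with fewer than three sessions. At the suggested sessions, the hypothetical participant above would have ratings at 2 and 6 and lack the one at 15, so 1 of 3 due ratings would be missing because of stopping.

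**The case against.** The strongest reply is that these are overlapping source lists. Coach documentation in 5.3 can include the 11.2 checklist, section 11.2 points onward to the process evaluation, and Table 6 has a coach row beside the diary row. Using coach and participant sources together is not in itself a contradiction. This stands, and a reader who inferred four rival definitions would go too far. What remains is the changing label on monitor data, diaries and attendance.

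A reader might also infer that the whole fidelity figure rests on ratings at therapist-chosen times. The documents do not support that, because the checklist covers every session.

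Nor does the 70% in section 14.3 predict how many intervention participants will miss a late rating. It is a precision example for the cohort of 120, not an expected rate for the 30 in the intervention arm.

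Self-report is also a defensible choice in a feasibility trial. Section 5.3 asks for coach documentation to be reviewed, section 11.1 provides training and ongoing monitoring, and section 12 adds interviews and completed visits. This largely stands, although 5.3 does not say who reviews and no section makes the monitoring a fidelity measure.

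Scoring rules may sit in a SAP or process evaluation plan that is not shown, so their absence is not counted here. The conflicting labels and the open timing are in the protocol itself.

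**Conclusion.** The point holds in a limited form. Monitor data, diaries and session attendance are assigned to fidelity in some places and to adherence in others, although section 5.3 makes these two separate primary outcomes. The self-assessment, and only that component, can be selected upwards and gives rating points that are not comparable between participants. The size cannot be computed from the documents, and the direction assumes that therapists tend to choose favourable moments, which the protocol permits but does not show.

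A reader might infer that this could tip the decision to proceed. It could not under the stated rules: section 15.1 sets no fidelity threshold, and its progression criteria use drop-out alone. The severity is therefore minor. The change is still worth making because it is cheap and affects how a primary outcome is reported.

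**What to change.** 1. Reconcile sections 5.3, 11.2 and 12 with Tables 3 and 6, so that coach delivery is fidelity, and FitBit data, diaries and sessions completed are participant adherence. Name the device meant in 5.3 and report how many participants have no FitBit upload.
2. Report as the main fidelity figure the proportion of all delivered sessions, early stoppers included, whose existing per-session checklist meets the manual. The home visit record can supply the count of delivered sessions. State that the figure is therapist-reported, and say who carries out the review in 5.3.
3. Make the self-assessment due at the protocol's own suggested sessions 2, 6 and 15, and report how many due ratings are missing because the participant stopped. A rule that the last rating falls at the participant's final session would not work prospectively: section 10.2 recognises loss to follow-up only after more than four consecutive missed sessions, when the final session has already passed.

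The cost is protocol wording; no new data are needed. Therapists lose freedom over when they rate themselves, and the checklist figure remains self-reported, so the change removes timing selection but not self-rating.

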# 11.3 Intervention comparator

#### Nested RCT

Those participants in the nested RCT randomised to activity as usual will not receive the physical activity intervention and will be asked to continue with their usual level of physical activity for the 12 month follow up period. They will not receive home visits from the intervention delivery staff (physical therapists), but they will be asked to record their activity monthly in paper diaries which will be sent to them. These participants will also receive monthly prompts via their preferred method of communication (e-mail/ telephone/ text messaging) to remind them to complete and return the diaries to their local coordinating centre in the stamped, addressed envelope provided. Their activity will not be monitored with the use of devices outside the week long activity monitoring period using Gene-activ devices that all participants will undertake.

# Observational Cohort

Outside of the baseline and 12-month assessments that will conducted in concert with scheduled annual Enroll-HD assessments, participants in the observational study will have no contact with research staff.

# 11.4 Defining 'activity as usual'

We will gather data on physical activity levels as well as use of health services as part of the trial assessments. This will give a representation of usual activity in all trial participants.

#### 12 Trial procedures

#### Recruitment and follow-up:

Participants will be assessed at baseline, at 6 months (for participants of the nested RCT only) and at 12 months. Those enrolled in the observational cohort (n=60) and those taking part in the nested RCT and randomised to the control arm (n=30) will continue to undertake physical activity as usual. Those participants in the nested RCT randomised to receive the intervention (n=30) will receive 12 months of an individualised physical therapy intervention, coached by a physical therapist.

#### Physical Activity Monitoring

All participants will undergo physical activity monitoring following their baseline and 12 month assessments. Activity will be monitored using Gene-activ devices (which are worn like a wrist watch) for a period of 7 days. Participants will be required to return the Gene-activ device to the site co-ordinator after the monitoring period in a pre-paid, padded envelope provided. Gene-activ devices are not interactive and so the participant will remain blind to the data that is being recorded by the device.

Participants randomised to the intervention arm of the nested RCT will be provided with FitBit Charge 2 device as part of the intervention. These interactive devices will enable participants to track their physical activity and activity goals for the duration of the trial. Data from the FitBit devices will automatically sync to FitBit servers and summary data exports on defined parameters will be sent to the trial team. FitBit devices will not need to be returned at the conclusion of the trial.

Additionally, participants in both arms of the nested RCT will be asked to complete monthly diaries of physical activity. This can be an on-line option (prompted by text message delivery of a link to the online form) or a paper based option, dependent on the preference of the participant.

Traditionally, monthly activity data has been collected using a calendar format accessible on-line or on paper. However, completion rates of these formats is typically low. We have designed a novel electronic user interface for participants to provide activity data with the aim of improving completion rates. To test the validity and usefulness of the new design, participants recruited to the RCT arm will be randomised to receive a link to either the existing on-line diary or the novel electronic diary. The implementation of this will not affect activity at sites. A separate Study Within a Trial (SWAT) protocol will be written to define the objectives, outcome measures, randomisation, implementation and analysis of this study.

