# Data collection/assessments and blinding

All data will be collected by researchers at site and will include but is not limited to; local Enroll-HD coordinators, clinicians and physical therapists delivering the intervention. All assessments will be performed at the research site. Intervention delivery data will be collected at the point of intervention delivery, be that at the research site or participant's home, depending on the participant's preference. Due to the nature of the intervention and the pragmatic design of the nested RCT, researchers collecting assessment data will not be blind to the allocation of participants.

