# Nested RCT

Participants will be assessed at baseline, 6 months and 12 months.

Table 1: Assessments additional to the standard Enroll-HD test battery for all sites:

Construct	Measure	Time to complete	Time points
Fitness	Predicted VO2 Max will be measured during stepwise incremental exercise test  . The test is performed on a cycle ergometer with participants seated in a standardized position. Participants will attempt to maintain a cadence of 50 revolutions per minute (rpm), starting at 50 Watts and increasing by 25	20 min	Baseline, 6 months (RCT only), 12 months

	Watts every two minutes until test termination. The test will be terminated when the participant reaches volitional exhaustion or cadence drops by 10 rpm. At the end of each increment, work-rate (Watts), rating of perceived exertion (Borg RPE scale) and heart rate will be recorded for analysis and conversion to predicted VO2 max score.		
Walking endurance	The 6-minute walk test will be used as a measure of walking endurance. This test evaluates the distance walked over a 6 minute period, and has been validated for use in HD  .	10 min	Baseline, 6 months (RCT only) and 12 months
Patient- reported clinical symptoms	HD Pro-Triad  will be used to assess disease specific symptoms including cognitive decline, emotional/behavioural dyscontrol and motor dysfunction.	10 min	Baseline and 12 months
Physical Activity Monitoring	Brunel Lifestyle Physical Activity Questionnaire  self-report instrument that measures the planned and unplanned dimensions of lifestyle physical activity.	5 minutes	Baseline
	Research-grade physical activity monitors (Gene-activs) will be used for a 7-day physical activity assessment .  Participants will be given the monitors at the consent visit, and will be asked to return them at the baseline visit one week later. They will be requested to wear them for 24 hours a day for the full week, except when showering. Participants will be given the monitors at the end of the assessments, and will be given addressed stamped mailing envelopes to return the monitors one-week later. Data obtained for analysis will include level of overall physical activity, sedentary behavior and sleep patterns. For validation of sleep time compared to sedentary time, participants will be asked to complete and return sleep diaries for the 7 day period of physical activity assessment.	5 min	Baseline, 6 months (RCT only) and 12 months

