	International Physical Activity Questionnaire (Short Form) will be used to assess 7-day physical activity, and to validate with the physical activity monitors. 	5 min	Baseline, 6 months (RCT only) and 12 months

Table 2: Assessments additional to the standard Enroll-HD test battery for RCT sites only

Construct	Measure	Time to complete	Time points
Motor and dual task function	The Clinch Token Transfer Test (C3T) is a dual-task assessment of bilateral, upper motor function that consists of three-coin transfer tasks which increase in difficulty (baseline simple, baseline complex and a dual task). The time taken to pick up and transfer the coins from dominant to non-dominant hand and	b	Baseline and 6 months

	place into a purpose developed box is recorded. The addition of cognitive load increases the task complexity.		
Motor Function	Q-motor was developed in TRACK-HD and TRACK-ON-HD where motor tasks are related to functionally relevant everyday tasks. All Q-Motor assessments are based on the application of pre-calibrated and temperature controlled force transducers and 3D position sensors with very high sensitivity and test-retest reliability across sessions and sites in a multicenter clinical trial.	10 min	Baseline and 12 months
Cognitive Function	Q-Cog was developed in TRACK-HD and TRACK-ON-HD where cognitive tasks are related to functionally relevant everyday tasks. Q-Cog assessments deploy the technology used in the Q-Motor system to benefit from the high accuracy of the sensors in tasks with high cognitive load. Again this offers high sensitivity and test-retest reliability across sessions and sites in a multicenter clinical trial.	20 min	Baseline and 12 months
Self- efficacy	The Lorig Self Efficacy  scale will be utilized to measure self-efficacy related to exercise (exercise sub-scale only)	5 min	Baseline, 6 months and 12 months

Table 3. Schedule of enrolment, interventions and assessments (from HRA CTIMP protocol template)

	Screening Baseline			Intervention	Follow Up	
IMEPOINT** (months)	minus 4 weeks to 0	1	Months 2-6	Month 6	Months 7-12	Month 12
NROLMENT (OBSERVATIONAL SITES)	11001111111					
Pre-screening from ENROLL-HD	x					
ligibility screen (records review)	x					
nformed consent		х				
Registration	+	x				
0						
MBEDDED RCT (3 SITES)	v					
Pre-screening from ENROLL-HD	X					
Eligibility screen (records review)		х	_			_
MUST malnutrition universal screening tool	X		-			
nformed consent	X	×	-			

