Physical Activity Readiness Quesionnaire (Par-Q) safety screening	-	х				
Registration		X			-	
Randomisation		Х				
INKED ENROLL-HD DATA (ALL SITES)						
Age		х				
ocal CAG high value		х				
Date of HD clinical diagnosis		х				
Ethnicity		х				
Gender		х				
Height		X				
Neight		×				×
	-	×				×
BMI	+	X				×
Medications	_		-		_	
Comorbidities	_	Х		_		X
Pharmacotherapy		х	-		-	X
Non-Pharmacologic Therapies		X				×
JHDRS TMS		х				X
UHDRS TFC		x				x
UHDRS Independence scale		х				х
UHDRS Function Assessment		x				х
Symbol Digit Modality test (numbers correct)		х				х
Verbal fluency category		х			1	x
		×	-		+	×
Letter Fluency	_	x			1	×
Trailmaking	_		_		1	x
Stroop word reading test		×	-	-	-	
Strrop colour naming		X		-	1	X
Stroop Interference		X			ļ	×
CSRI		X				X
HADS-SIS		X				X
Problem Behaviours Assessment (apathy sub domain)		х				х
SF12		х				х
TUG		х				х
30 sec chair stand		x				x
Medication changes since last visit		×	1			x
Event Reporting		-	_	1		x
PACE-HD STUDY DATA (ALL SITES)		u u				×
Physical Fitness predicted VO2		X	_	-		_
6 minute walk test	_	X		-		X
HD Pro Triad		х	-	-		X
Brunel lifestyle physical activity questionnaire		х				-
7 day accelerometer based physical activity assessment with sleep diary (debrief		×				×
interview over phone)		+				×
Self reported physical activity (iPAQ short last 7 days, telephone format)	_	×	+			-
Event Reporting						
PACE-HD STUDY DATA (RCT ONLY)						
Physical Fitness predicted VO2		Х		X		Х
7 day accelerometer based physical activity assessment with sleep diary (debrief						·
interview over phone)		Х		х	-	X
Self reported physical activity (IPAQ short last 7 days, telephone format)		X		х		Х
C3T		Х		х		
Q Motor assessment battery		×				х
Q Cog assessment battery		х				х
Lorig Self Efficacy Scale (exercise domain)		X		х		х
PHYSICAL INTERVENTION						
		×	XXXX		XXXX	
Delivery of physical intervention (home visits)	_	_		_	XXXX	
Text messaging prompts		X	XXXX	+		1
Activity monitoring data to record adherence to intervention (FitBit activity data)		Х	X	-	X	-
Telephone review (Health and Falls Record)		х	X	X	х	-
Adverse event assessments		X	х	х	х	x
USUAL CARE						V
Telephone review (Health and Falls Record)		x	х	х	х	
						-

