#### Nested RCT

The intervention phase will be followed by a follow-up period which will continue for one week after the last participant completes the intervention. This follow up will consist solely of activity monitoring using a wrist worn monitoring device (e.g. an activity watch). On conclusion of this week long monitoring period, the participant's involvement in the trial will end.

The end of the trial is defined as the date of final data capture to meet the trial endpoints. In this case end of trial is defined as upload of the final activity monitoring data into the trial database. Sponsor must notify the local IRBs of the end of a clinical trial in accordance with local requirements.

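### The protocol does not ensure that the IPAQ recall week and the Gene-activ wear week are the same week, although one is to be validated against the other

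*Protocol*

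**What the plan says.** **The comparison.** Section 12.1, Table 1, says the IPAQ short form "will be used to assess 7-day physical activity, and to validate with the physical activity monitors". Section 15.2 plans, among the exploratory analyses, to set self-reported activity against the Gene-activ data. The Synopsis lists both measures as secondary outcomes.

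**The wear week.** Section 12, Physical Activity Monitoring: "All participants will undergo physical activity monitoring following their baseline and 12 month assessments" and "Activity will be monitored using Gene-activ devices (which are worn like a wrist watch) for a period of 7 days". Section 12.1, Table 1, first says: "Participants will be given the monitors at the consent visit, and will be asked to return them at the baseline visit one week later". It then says, without naming a time point: "Participants will be given the monitors at the end of the assessments, and will be given addressed stamped mailing envelopes to return the monitors one-week". Tables 1 and 3 also list a 6-month wear week for the RCT, which the Section 12 sentence does not mention.

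**The IPAQ.** Table 3 has "Self reported physical activity (iPAQ short last 7 days, telephone format", next to an accelerometer entry that carries its own debrief by phone. Section 12, Data collection/assessments and blinding, says: "All assessments will be performed at the research site". Section 16.1.1 lists the IPAQ among the baseline, 6-month (RCT) and 12-month assessment forms, to be completed as the data are collected.

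**The end of the trial.** Section 18, Nested RCT: "The intervention phase will be followed by a follow-up period which will continue for one week after the last participant completes the intervention". That week contains activity monitoring only, and Section 13.4.1 does not require SAE reporting during it.

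**The concern.** A 7-day recall questionnaire can be validated against a 7-day monitor only if both describe the same days. When they do not, real week-to-week variation in activity is counted as measurement disagreement, and the IPAQ may look less valid than it is.

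The present text lets two sites follow different parts of the protocol and produce pairs that are not comparable. The same site could also produce matched pairs at one time point and unmatched pairs at another. A wear week that was not recorded cannot be recovered at analysis.

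A second matter concerns interpretation. FitBit data exist only in the intervention arm, so Gene-activ is the only device-measured activity outcome in both arms of the RCT. At month 12 it is recorded after the visit and after the intervention phase. Someone reading an effect estimate for a 12-month programme could take it to describe activity during coaching unless the report says otherwise.

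**Working it through.** The plan gives no figure for this comparison. Its one calculated figure, the precision of a 70% retention rate with n = 120, reproduces: 1.96 × √(0.7 × 0.3 / 120) = 0.082, that is ±8.2%. It does not bear on this point. The check here is a count of shared days.

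**Inputs.** Wear length 7 days (Section 12). Recall length 7 days (Table 3). Wear position: after the visit (Section 12), or before it at baseline (Table 1). IPAQ day: not stated. Call it q, in days after the visit, and show a range.

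**Wear after the visit.** Wear covers days 0 to 7 and recall covers days q − 7 to q. Shared days = max(0, min(7, q) − max(0, q − 7)).

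| IPAQ day q | Shared days of 7 |
|---|---|
| 0 (at the visit) | 0 |
| 1 | 1 |
| 3 | 3 |
| 7 (call at end of wear) | 7 |
| 10 | 4 |
| 14 | 0 |

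**Wear before the visit** (Table 1, consent to baseline). Wear covers days −7 to 0. With the IPAQ at the visit, recall also covers −7 to 0, so 7 of 7 days are shared. With a call on day 7, recall covers 0 to 7, so shared days = min(0, 7) − max(−7, 0) = 0.

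**Side by side.** An IPAQ at the visit matches the Table 1 baseline week fully and the Section 12 post-visit week not at all. A call one week later does the reverse. If Table 1 governs baseline and Section 12 governs month 12, no single IPAQ day relative to the visit gives full overlap at both.

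**Pairs concerned.** With complete data: 120 participants × 2 time points (baseline, month 12) = 240, plus 60 RCT participants at month 6 = 60, giving 300 planned pairs.

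**Month 12.** Section 12 puts the wear week after the assessment. Section 18 puts a week of monitoring after the intervention phase. Section 13.4.1 takes that week out of SAE reporting. All three are consistent with a wear week after coaching has ended, for the 30 participants randomised to the intervention.

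**The case against.** The strongest reply is that Table 3 is the only place that says how the IPAQ is given. It says by telephone, next to a phone debrief for the monitor, so a call at the end of wear with full overlap may be what was intended. Section 16.1.1 does not contradict this, because a telephone interview entered as it happens still meets real-time entry. The sentence on site-based assessment cannot be literal for a week of monitoring away from the site.

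Much of this stands. A reader might infer that the validation definitely compares different weeks. The documents do not support that, because no passage dates the IPAQ. But neither does any passage place the call at the end of wear, and Table 1 and Section 12 still disagree about the baseline week.

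A reader might also infer that the month-12 activity outcome is wholly off-intervention. That too goes too far. Section 12 lets intervention participants use the FitBit for as long as the trial lasts (Section 11.1 says throughout the 12 months). Eighteen sessions over 52 weeks is about one every 52 / 18 = 2.9 weeks, so many weeks within the programme have no session either. Measuring just after the last contact is a defensible end-of-programme assessment, and the RCT has a 6-month wear week during the intervention.

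Nor is Gene-activ shown to be free of bias: participants cannot see its data, but they know their allocation.

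**Conclusion.** The concern holds in limited form. The protocol does not secure a common week for the IPAQ and the monitor. The overlap ranges from 0 to 7 of 7 days, depending on an IPAQ day that is not stated and a wear-week position that is stated in two ways at baseline. The comparison may therefore use different weeks, and may do so differently by site and time point. The 0-of-7 result assumes post-visit wear with the IPAQ at the visit; the 7-of-7 result assumes post-visit wear with a call on its last day, or pre-visit wear with the IPAQ at the visit.

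The loss of agreement between the two measures cannot be sized from the protocol, which gives neither a same-week correlation nor the week-to-week reliability of activity.

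The month-12 Gene-activ value is a post-coaching measurement. That calls for a clear label and is not in itself an error. The consequences reach a secondary outcome and an exploratory analysis. The primary feasibility outcomes are unaffected, and no formal hypothesis testing is planned.

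**What to change.** 1. State one position of the wear week relative to the visit at baseline, month 6 (RCT) and month 12, and make Section 12 (Physical Activity Monitoring), Table 1 and Section 18 agree.
2. Give the IPAQ on the last day of that wear week, in one stated mode, at every time point where both are collected. The debrief call already in Table 3 is a natural place for it.
3. Amend the site-assessment sentence in Section 12, Table 3 and the form list in Section 16.1.1 to match.
4. State in the analysis and the report that the month-12 Gene-activ value is measured in the week after coaching ends, and that FitBit use may continue during it.

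The cost is wording in these places. If wear stays after the visit, the IPAQ also moves off the visit day by up to a week. Moving the month-12 wear week before the visit is optional: it would bring the week closer to the programme but would require devices to be sent out beforehand, and steps 1 to 4 do not depend on it.
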